5.7.5 Other criteria

- The evolution of AFP rates over time.

5.7.6 Exploratory analyses

Not Applicable

5.7.7 Management of criteria between la phase II and la phase III

The common criteria for la phase II and la phase III (Section 5.7.2 and 5.7.4.) will be reviewed at the end of la phase III, or at the end of la phase II if la phase III is not performed. If these criteria are only assessed in la phase II, there will be no comparison made between arms.

In order not to introduce operational bias, all criteria can be described in la phase II (common or not to la phase III), but the common criteria must remain confidential.

In all cases, a description of the TACE treatment and a description of the catch-up treatments will be made.

6 Study populations

The study focuses on patients with hepatocellular carcinoma.

6.1 Definition of Analysis Populations

6.1.1 Intent-to-treat (ITT) population

The intention-to-treat population is defined as all patients included in the study, regardless of eligibility criteria and amount of treatment taken.

The description of the population at inclusion will be based on this population.

6.1.2 Modified intention-to-treat population (mITT)

The modified IIT population is defined as all patients included in the study, regardless of eligibility criteria and amount of treatment taken who had at least one chemoembolization.

The primary endpoint will be assessed in this population.

6.1.3 Population for Tolerance Analysis (SP)

It is defined as la population ITT that received at least one day of treatment with sunitinib/placebo (no constraints on chemoembolization).

The analysis of secondary efficacy endpoints will be done in this population (depending on the randomization arm)

Patients who did not take treatment will be described by individual data.

The analyses for tolerability will be performed according to the actual treatment received. Thus, if despite randomization, a patient received placebo instead of sunitinib from baseline to the end of treatment, this patient will be analyzed for safety in the placebo arm (and vice versa).

However, if a change of treatment (sunitinib/placebo) occurs during treatment, the patient will be analyzed in the group corresponding to the first treatment he/she received.

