5.7 Judgement criteria for la phase II

5.7.1 Main criterion

The primary endpoint of la phase II is the rate of bleeding and/or severe liver failure within one week of chemoembolization sessions (TACE), over all chemoembolization sessions for a patient. The precise definition of bleeding and liver failure to be retained is given in the protocol with amendment 3 :

- Severe liver failure is defined by the occurrence of at least one of the following complications:
 - encephalopathy;
 - clinical ascites; in case of clinical ascites already present at inclusion and persistence of ascites at the time of evaluation for liver failure, an independent committee will have to judge from the case report whether ascites has evolved since inclusion and should be counted as an event in the definition of the primary endpoint or not; if clinical ascites is present at inclusion, it will be graded according to NCI-CTC v4 and reported through a CID; during follow-up, clinical encephalopathy and ascites will be graded according to NCI-CTC v4 and will appear on form 3.1 of the case report form in the other toxicities tab
 - bilirubin levels greater than or equal to 50 mg/L (85.5 μ mol/L);
 - TP \leq 40%;
- bleeding : (definition p14 of the protocol)

These events count as primary endpoints if they occur within 1 week of chemoembolization, i.e., between D0 and D7 inclusive.

In the case of an event counting for the primary endpoint after D7, it will be recorded in the case report form 3.1 in the column after D5 only if the investigator considers that this event is related to the TACE, and the day must then be filled in. For events recorded after D7 in the case report form, an independent committee will meet to decide whether or not this event counts in the definition of the primary endpoint.

Patients who did not receive their oral treatment will still be counted in the primary endpoint; however, a very precise description of the reason for not taking the oral treatment will be made.

Patients who did not have chemoembolization will be excluded from this analysis (modified ITT).

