7.2.3.2 Final Analysis

The point date for the final analysis is the 130th event.

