8.7.1 Progression-free survival

Progression-free survival will be compared between the 2 treatment groups (Phase III) or described (Phase II) using the stratified logrank test and using the simple logrank test.

The estimation of treatment-related hazard ratios will be performed using a stratified Cox model (Cox, 1984);

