8.7.2 Overall survival

Overall survival will be compared between the 2 treatment groups (Phase III) or described (Phase II) using the stratified logrank test and using the simple logrank test.

The estimation of treatment-related hazard ratios will be performed using a stratified Cox model (Cox, 1984);

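### SAP 6.1.3 restricts secondary efficacy to dosed patients, against the protocol's intention-to-treat rule, and the SAP names no population for phase III overall survival

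*SAP*

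**What the plan says.** The protocol states its rule twice. Section XVI (Phase III step) has the main and secondary objectives analysed by intention to treat on every enrolled patient. Section XVII makes ITT the primary set for efficacy. It places the exclusion of never-dosed patients in the per-protocol set and uses the at-least-one-dose set for safety data.

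The SAP distributes its populations differently:

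- 6.1.1, ITT: "The description of the population at inclusion will be based on this population". No other use is given.
- 6.1.2, mITT (at least one chemoembolization): "The primary endpoint will be assessed in this population". The phase is not named. Section 5.7.1, on the phase II toxicity endpoint, says "Patients who did not have chemoembolization will be excluded from this analysis (modified ITT").
- 6.1.3, SP (at least one day of study drug): "The analysis of secondary efficacy endpoints will be done in this population (depending on the randomization arm").

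The phase III tests are in 8.7. Section 8.7.1 reads "Progression-free survival will be compared between the 2 treatment groups (Phase III) or described (Phase II") and 8.7.2 reads "Overall survival will be compared between the 2 treatment groups (Phase III) or described (Phase II"). Both name stratified and simple logrank tests and a stratified Cox model. Neither names a population.

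**The concern.** Leaving out randomised patients because they never took study drug departs from the comparison that randomisation protects. Here it also contradicts the governing protocol, and the SAP gives no reason. An analyst following the protocol and one following the SAP would report the secondary efficacy endpoints on different sets.

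The gap for overall survival is of another kind. It is an omission, but it concerns the confirmatory test, whose analysis set should be fixed in advance. If the unqualified wording of 6.1.2 were applied to overall survival, the set would depend on having had a chemoembolization. Study drug starts 7 to 10 days before that procedure (Protocol IX), so it could influence who has one. Exclusion could then differ by arm.

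**Working it through.** **1. The populations side by side**

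| Set | Protocol XVI–XVII | SAP 6.1 |
|---|---|---|
| All randomised (ITT) | All efficacy and baseline data | Description at inclusion only |
| At least one dose | Safety data | Tolerance and secondary efficacy |
| At least one chemoembolization (mITT) | Not defined | The primary endpoint, phase not named |

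Never-dosed patients are expected. SAP 6.1.3 has them described individually. SAP 5.7.1 still counts patients who did not take the oral treatment in the phase II toxicity endpoint, provided they had a chemoembolization. Such a patient counts for toxicity and drops out of secondary efficacy, which reverses the protocol's scheme.

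**2. Which population applies to phase III overall survival?** The SAP supports two readings and states neither.

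- mITT: 6.1.2 speaks of the primary endpoint without a phase, and 5.5.3 uses the same term for phase III overall survival. Against this, 5.7.1 and 8.4 tie mITT to the phase II toxicity endpoint.
- SP: overall survival is defined only in 5.7.2.5, under the secondary efficacy criteria, and 5.7.7 treats the 5.7.2 criteria as common to both phases.

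Neither is the protocol's ITT.

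**3. The plan's own phase III figures.** Inputs (SAP 5.5.3): 2-year survival 40% and 60%, two-sided alpha 0.05, power 90%, 2 years of uniform accrual plus 3 years of follow-up, 5% attrition.

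- HR = ln(0.60)/ln(0.40) = 0.557 (stated 0.56).
- Freedman: events = (1.960 + 1.282)² × [(1 + 0.557)/(1 − 0.557)]², giving 131 rounded up (stated 130).
- Mean probability of death under exponential survival = (0.834 + 0.636)/2 = 0.735, so 130/0.735 = 177 patients (stated 180).
- 180/0.95 = 189.5, so 190 (stated 190).

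These calculations count all included patients, so specifying ITT leaves 130 events and 190 patients unchanged.

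**4. Scale of the difference.** The documents give no never-dosed rate and no planned rates for the secondary endpoints. The overall survival figures are the only planned ones, so they serve as a yardstick. With 190/2 = 95 per arm, 0.60 × 95 = 57 and 0.40 × 95 = 38 patients are alive at 2 years.

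- Leave out one sunitinib patient who died before 2 years: 57/95 = 60.0% becomes 57/94 = 60.6%.
- Leave out one such placebo patient: 38/95 = 40.0% becomes 38/94 = 40.4%.

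Now let a fraction f be never dosed, equal in both arms, with no drug effect in those patients. Then the ITT difference = (1 − f) × the SP difference. Taking 20 points in SP:

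- f = 1%: 0.99 × 20 = 19.8 points.
- f = 5%: 0.95 × 20 = 19.0 points.

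The gap is 0.2 to 1.0 points. The 1–5% range is an assumption.

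**The case against.** The strongest reply is that this is mainly a phase II plan. Section 5.7 is headed for phase II, the survival endpoints are defined for the case that phase III is not done, and the forecast in 9.2.2 lists only phase II. In that case arms are not compared: "If these criteria are only assessed in la phase II, there will be no comparison made between arms". Phase III overall survival would then fall under the protocol's ITT rule, which the SAP nowhere revokes. This limits the point but does not answer it. Section 5.7.7 carries the 5.7.2 criteria into phase III, 8.7 states that arms are compared there, and 5.5.3 fixes the phase III events and thresholds.

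The scope can also be questioned. Only progression-free and overall survival have a stated test. Tumour control gets Kaplan-Meier percentages, disease-free survival has no subsection in 8.7, and the protocol does not name progression-free survival. These are fair observations. However, the protocol's rule covers all efficacy data, and 6.1.3 applies to every secondary efficacy endpoint.

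SP does keep the randomised arm, and blinding limits selective exclusion, so the bias is probably small. The figures in step 4 show dilution between two populations, not a measured bias. The mITT reading of overall survival is the less likely one. Finally, the SAP cites a protocol amendment whose liver-failure criteria differ from the protocol text in hand, so the versions may not match fully. Nothing suggests that an amendment changed the populations.

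**Conclusion.** The concern holds. SAP 6.1.3 states a rule that contradicts Protocol XVI and XVII, and it should be corrected. The missing population for phase III overall survival is an omission; alone it would be missing detail.

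The numerical effect is not established. Under the assumptions in step 4 (1–5% never dosed, balanced, no drug effect in them) it is 0.2 to 1.0 points on a 20-point difference. It would be larger only if overall survival were analysed in mITT, which 5.7.1 and 8.4 make unlikely. No loss of power is claimed, since SAP 7.2.3.2 says "The point date for the final analysis is the 130th event". The conflict bears on between-arm results only if phase III takes place.

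**What to change.** - **SAP 6.1.1:** state that overall survival (primary in phase III), progression-free survival, disease-free survival and tumour control are analysed in all randomised patients, by randomised arm.
- **SAP 6.1.2:** specify that mITT applies to the phase II primary endpoint.
- **SAP 6.1.3:** limit SP to tolerance, and label any efficacy analysis in SP or mITT as a sensitivity analysis.

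This costs a few lines of text and needs no new data, patients or events. SAP 7.3 requires such changes before the database is frozen.

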6.2 Definition of analysis subgroups

Not applicable

7 Recruitment and analysis planning

7.1 Recruiting

The expected rate of inclusion is 7 to 8 patients per month.

7.2 Analysis planning

7.2.1 Pilot phase

The analysis of the pilot phase was conducted in April 2011.

7.2.2 Phase II

The cut-off date for the la phase II analysis will be one week after the completion of the last chemoembolization of the last included la phase II patient.

7.2.3 Phase III

7.2.3.1 Intermediate Analysis

An interim analysis is planned during la phase III. This analysis is planned at the midpoint of the number of events, i.e. at 65 deaths. Based on the assumptions made, this analysis could take place 28 months after the inclusion of the first patient.

7.2.3.2 Final Analysis

The point date for the final analysis is the 130th event.

7.2.3.3 Late analysis after Phase III

A final analysis will be performed to account for overall survival at 4 years. The time point is 4 years after inclusion of the last patient.

7.2.4 Transition from Phase II to Phase III

In case of transition to phase III, only results concerning the primary endpoint, safety data, and control rates during each TACE will be reported for la phase II

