3.2.2.2 Secondary objectives

The secondary objectives of the phase II study are to evaluate:

- tumor control rate* at 3, 6, 9 months after the last TACE ;
- Progression-free survival
- Overall survival*;
- Tolerance*;
- Quality of life*.

*These objectives are common objectives with la phase III

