8.5.1.2 Response to treatment during treatment

For each of the TACE numbers (1, 2, 3 or more) will be described:

- The overall response to TACE for treated target lesions and/or for treated non-target lesions;
- the number of TACE followed by at least one new liver injury
- The number of TACE followed by at least one new extrahepatic lesion;
- The number of TACEs with the development of a second cancer, and the number of TACEs requiring additional TACE),

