8.7 Criteria common to la Phase II and la Phase III

These endpoints will only be studied in la Phase II if la Phase III not occur. Comparisons between arms will only be made in Phase III.

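### On transition to phase III, SAP 7.2.4 puts per-TACE control rates, described by arm, into the phase II report, although SAP 5.7.7 keeps the criteria built on the same assessments confidential

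*SAP*

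**What the plan says.** - **SAP 7.2.4**, which applies only when the trial passes to phase III: "only results concerning the primary endpoint, safety data, and control rates during each TACE will be reported for la phase II". It does not define the control rates, say who receives the report, or say whether results are pooled or by arm.
- **SAP 3.2.2.2** lists "tumor control rate* at 3, 6, 9 months after the last TACE" among the phase II secondary objectives. The asterisk means: "These objectives are common objectives with la phase III".
- **SAP 5.7.7** takes the common criteria to be those of sections 5.7.2 and 5.7.4 and places their review at the end of phase III, or at the end of phase II if there is no phase III. It lets every criterion be described in phase II, "but the common criteria must remain confidential", and gives avoidance of operational bias as the reason.
- **SAP 5.7.2.1**, inside section 5.7.2, sets the RECISTm rules for evaluations after each TACE and for later follow-up. It applies them to progression-free survival, disease-free survival and tumour control.
- **SAP 8.5.1.2** describes, for each TACE number, "The overall response to TACE for treated target lesions and/or for treated non-target lesions". SAP 8.5.1 makes the chemoembolization description by treatment group.
- **SAP 8.7**, on the common criteria (timed tumour control is 8.7.3): "These endpoints will only be studied in la Phase II if la Phase III not occur".
- **SAP 9.2.2** lists the main criterion and the tolerance criteria for the phase II analysis on the frozen database.

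**The concern.** SAP 5.7.7 identifies a risk and sets a rule against it: efficacy criteria that also count in phase III stay confidential while the trial runs. SAP 7.2.4 then allows a tumour-response result into the phase II report in the one situation where that rule matters, namely when phase III goes ahead.

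The 70 phase II patients are kept in the phase III analysis and most of the trial is still to be recruited. If by-arm control rates became known to investigators, they could influence which patients are entered, how readily TACE or study drug is continued, and when other treatment is started. Those choices feed into progression-free survival, disease-free survival and tumour control and, through later treatment, possibly overall survival, the phase III primary endpoint.

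**Working it through.** **1. Patients involved (SAP 5.5.3, 7.1).** The plan's own figure is reproduced: 190 − 70 = 120 patients still to be included. The share already seen is 70/190 = 36.8%. At the expected 7 to 8 inclusions per month, the remaining 120 take 120/8 = 15 to 120/7 = 17.1 months.

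**2. What a per-TACE control rate is made of.** The only rule in the SAP for judging response after a TACE is the first part of 5.7.2.1. A treated lesion that progresses, or a new lesion, is a progression there. It is therefore also an event for progression-free survival under 5.7.2.3. Control rates per TACE would thus show early progression in patients of the phase III analysis.

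**3. By arm or pooled.** SAP 8.5.1 specifies treatment group, and 8.1.6 makes separate description of each arm the default. Nothing in 7.2.4 departs from this.

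**4. The sections side by side, when phase III proceeds.**

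| SAP section | Treatment of control data |
|---|---|
| 7.2.4 | Per-TACE control rates are reported |
| 5.7.7 | Section 5.7.2 criteria may be described but stay confidential; reviewed at the end of phase III |
| 9.2.2 | Frozen-database phase II analysis: main criterion and tolerance only |
| 8.7 | Common endpoints, including timed control, not studied at phase II |

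**5. Whether the decision needs them.** The rule in SAP 5.6.2 counts patients with severe bleeding or liver failure: at most 7, or 8 or more, of 35 on sunitinib, then the placebo count. No tumour result enters it.

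**6. How the per-TACE rate relates to the timed endpoint.** Protocol IX starts study drug 7 to 10 days before TACE and spaces courses 6 to 8 weeks apart. Protocol XI images one month after each course. With d the day of the first TACE, g the gap in weeks, k the course number and 30.4375 days per month (SAP 8.1.2), the scan after course k falls at (d + 7g(k − 1) + 30.4375)/30.4375 months from the start of study drug:

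- course 1: 1.2 to 1.3 months
- course 2: 2.6 to 3.2 months
- course 3: 4.0 to 5.0 months

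The first time point in SAP 3.2.2.2 is three months (91.3 days) after the last TACE:

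- two courses: (49 + 91.3)/30.4375 = 4.6 to (66 + 91.3)/30.4375 = 5.2 months
- three courses: (91 + 91.3)/30.4375 = 6.0 to (122 + 91.3)/30.4375 = 7.0 months

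On that clock the per-TACE scans come earlier than the first timed control point. The two measures share patients and part of the response data, but they are not the same quantity.

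**The case against.** The best defence is that 7.2.4 refers to something other than the protected endpoint. The starred objective is control at set months, whereas 7.2.4 speaks of control around each TACE, which fits the description in 8.5.1.2. That section lies outside 8.7, so the bar in 8.7 does not directly reach it. SAP 5.7.7 also provides for a description of the TACE treatment in every case. SAP 5.7.3 lists chemoembolization under tolerability, so the tolerance row in 9.2.2 might already include it. Moreover, the assessments after TACE count mainly treated lesions, while later ones count all lesions.

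Most of this stands, and it limits the point. A reader might infer that the SAP discloses the three-month control rate, because the scan after the second TACE falls about three months from the start of study drug. The documents do not support that: SAP 3.2.2.2 counts from the last TACE, and 5.7.2.2 states no starting point. It does not remove the conflict with 5.7.7, which covers all of section 5.7.2 and so includes the post-TACE rule in 5.7.2.1. A description of TACE treatment also matches 8.5.1.1 more naturally than the response results in 8.5.1.2, and the SAP files both under effectiveness.

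A reader might also infer that investigators will see the rates, or that they come out during active recruitment. SAP 7.2.4 names no audience, and a report to the independent committee alone would satisfy 5.7.7. SAP 5.6.4 suspends inclusions while phase II is analysed. The supportable statement is that the data may be reported before the remaining 120 patients are enrolled.

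There are safeguards. Individual patients stay blinded (SAP 5.3), an external radiology panel reviews the scans (protocol XI), and clinical progression does not count for progression-free survival (SAP 5.7.2.3). These protect the reading of a scan. They do not protect decisions on enrolment, continuation or later treatment once arm-level results are known.

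**Conclusion.** The point holds as a conflict within the SAP that should be resolved before any transition to phase III. Read as written, 7.2.4 allows early efficacy data by arm, from 37% of the phase III population, to be reported before the other 63% (120/190) are enrolled. SAP 5.7.7 calls for such data to remain confidential, and the phase II decision does not use them.

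This rests on three assumptions: that the phrase in 7.2.4 means response at the post-TACE assessments, that the default by-arm description applies, and that the report may go beyond the independent committee. If the report is for the committee only, the risk of bias largely disappears and what remains is missing wording. The 37% is a share of patients, not a measure of bias; the documents give no basis for estimating bias. The SAP cannot be said to release the timed tumour control endpoint itself.

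**What to change.** In SAP 7.2.4, strike the control rates so that the phase II report covers the primary endpoint and safety, in line with 9.2.2. Alternatively, keep them but define the measure and limit it to a confidential report to the independent committee.

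In SAP 8.5.1.2, add that if phase III proceeds, TACE response by arm is withheld from investigators and the sponsor's trial team until the phase III analysis.

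The cost is SAP wording only, and SAP 7.3 allows changes before the database is frozen. The small downside is that the phase II report carries no response data while phase III runs. Sample size, decision rule and data collection are unaffected.

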7.3 Adjustments

Adjustments may be made to this analysis plan in case of amendments to the protocol, or if phenomena not initially foreseen require statistical adaptations. In all cases, these modifications must be made before the database is frozen.

8 Statistical methods

Statistical analyses will be performed by the CRGA.

